7.6.4. Interim or Off-cycle Visits

Because this is an online observational study, we do not anticipate any interim visits to occur that are related to participating in the study.

7.6.5. Early Discontinuation

Incomplete surveys will be excluded from the analysis. Persons who are not verified as participants in the CFFPR between 2010 and 2018 will be excluded.

7.7. Sample Size

During the pilot phase, the study team will further discuss the statistical plan to ensure adequate numbers of participants are enrolled in the study. Based on information from participating centers, we expect to enroll approximately 600 women and expect about half of them to be on hormonal contraceptives based on our pilot study. The following table shows the power for detecting different RRs of non-hormonal to hormonal contraceptives in women and baseline proportion of outcome in the non-hormonal contraceptives group.

Table 8: Sample size calculation

	Using Poisson Regression Power to detect a Rate Ratio (hormonal / non-hormonal)
Total Sample Size	RR=0.70
450	0.77
475	0.80
500	0.82
525	0.83
550	0.85
575	0.86

CASE.4.CF Study Protocol

Recent data following the U.S. FDA approval of genetic modulators, show that in this population (mean age 25 years) there are approximately 0.8 PEx/year (13). Using Poisson regression, this study will have 80% power to detect a rate ratio of 0.70 between the progestin-only and combined hormonal groups with 575 enrolled women with CF (assuming alpha 0.05 and an estimated attrition rate of 15%). Although triple therapy has already been FDA approved, we do not anticipate this will affect our retrospective study design since we are evaluating years prior to FDA approval of triple modulator therapy.

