2.0. Background/Rationale

Family planning decisions are increasingly important for women with CF as most reach reproductive age in reasonable health. As CF care management and directed therapies advance, the number of women with CF in the US over age 18 has nearly doubled over the last 15 years: from 4,000 to 7,200. The CFF has an existing comprehensive patient registry, the CFFPR, which captures annual data on over 90% of all persons with CF in the US (1). While it is comprehensive regarding most aspects of CF patients' health, the CFFPR currently only asks one question that addresses reproductive health for women over 18 living with CF: "Was the patient pregnant during the reporting year?".

Reliable information is urgently needed to enable healthcare providers to help CF women understand the effectiveness and safety of current contraceptive methods for them. While infertility usually affects men with CF, at least 50% of women with CF are estimated to be physiologically capable of becoming pregnant without fertility treatment (2); however, that percentage is expected to rise with the use of new life sustaining medications, such as the CFTR modulators and especially the newly Food and Drug Administration (FDA)-approved triple-combination modulator, TRIKAFTA® (3).

Our recently completed survey study among 150 women at three CF centers, suggests that only about 60% of reproductive—aged women with CF are using contraception (4). Among those who are, oral contraceptive pills (OCPs) and condoms are the most commonly reported methods. Gaps in quality contraceptive care for women with CF exist, in part because, surprisingly, women with CF prefer to receive their sexual health care within the CF clinics, but many CF providers do not feel prepared to deliver safe and detailed contraception care (5). This information gap is exacerbated by the limited data which exist to inform contraceptive care provision for women with CF. In fact, most studies evaluating contraceptive safety are limited to oral contraceptive pills, even though the number of choices of FDA-

CASE.4.CF Study Protocol

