4.0. Study Objectives

4.1. Primary Study Objective

• To assess the association of hormonal contraceptive use on frequency of pulmonary exacerbations, compared to non-hormonal contraceptive users (primary control) and non-contraceptive users (secondary control).

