9.3. Statistical Methods

Because this is a retrospective cohort study, we are most interested in determining whether this exposure (to hormonal contraception) is associated with our primary outcome (counting the number of pulmonary exacerbations requiring additional IV in a given year) and/or our secondary outcomes (new respiratory microbiology, liver disease/non-cirrhosis, gallstone, requiring surgery/procedure, improved BMI, incidence of VTE, osteoporosis and fragile bone fracture). Women on hormonal contraception will be compared to the primary control group of women on non-hormonal contraception. We will also compare to women on no contraception, as the secondary control group. We will exclude persons with these existing diagnosis at the start of the follow up period for outcome data (January 1, 2010). Within this objective we will be able to calculate incidence rates, relative risks and confidence intervals. We will use Poisson regression to calculate progestin-only and combined hormonal method to non-hormonal method pulmonary exacerbation rate ratios and 95% confidence intervals. This allows for adjustment of follow-up time of each individual.

(Objective 1a): We will evaluate lab values over time (ppFEV1%, serum AST, ALT, alkaline phosphatase) to determine if trends between hormonal contraceptive users and non-hormonal contraceptive users differ. See Table 5 for confounders and covariates that we will use to adjust for the primary and secondary outcomes.

We will model ppFEV1 via generalized estimating equations (GEE), allowing for correlation within a subject, and compare via a fixed effect for exposure. Among women who change or stop contraception, we will estimate and compare within-participant difference in outcomes via the model (if numbers allow). We will censor women who switch method types or become pregnant, and for 6 months post pregnancy, for the primary analysis and subsequently follow them to leverage within-patient data and analyze changes in pulmonary status and contraception. Presence of respiratory microbiology will be estimated longitudinally via GEE with a logit link function. Graphic displays and summary statistics will be used; all *p* values will be two-sided.

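### Section 7.7 claims 80% power for progestin-only versus combined, but on the one-year basis that reproduces Table 8 that contrast has about 0.62, and no split, follow-up or dispersion is stated

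*Combined protocol and SAP*

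**What the plan says.** - Section 4.1 compares hormonal users on exacerbation frequency, "compared to non-hormonal contraceptive users (primary control) and non-contraceptive users (secondary control". Non-users are therefore a separate group from the primary control. Section 8.1 also lists three groups, the third being women who never used contraception.
- Section 7.7 expects about 600 women and says the team "expect about half of them to be on hormonal contraceptives based on our pilot study". Table 8 is headed "Power to detect a Rate Ratio (hormonal / non-hormonal" and is indexed by total sample size. Stated power is 0.77, 0.80, 0.82, 0.83, 0.85 and 0.86 at 450, 475, 500, 525, 550 and 575 women.
- The text below the table claims "80% power to detect a rate ratio of 0.70 between the progestin-only and combined hormonal groups with 575 enrolled women with CF". It takes a 5% significance level and 15% attrition, and cites about 0.8 exacerbations per year.
- Section 9.3 estimates rate ratios for progestin-only and for combined methods, each against non-hormonal methods, and says that p "values will be two-sided".
- Section 2.0 reports that an earlier survey of 150 women "suggests that only about 60% of reproductive"-aged women with CF use contraception. Section 7.2 describes the study population as women who have used some form of contraception.

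**The concern.** Three contrasts are in play: pooled hormonal versus non-hormonal (Table 8), progestin-only versus combined (the 80% sentence), and each type versus non-hormonal (Section 9.3). They use different numbers of women, so one total sample size will not in general give them the same power. Section 7.7 nevertheless attaches about 80% at a rate ratio of 0.70 to the first two and gives nothing for the third.

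The plan also gives no size for the primary control. If half the women are hormonal users and a secondary control of non-users exists, the other half cannot all be primary controls. A reader therefore cannot tell which comparison is powered. A null result for one hormonal type might be read as evidence of no effect on the strength of an 80% figure calculated for something else.

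**Working it through.** **Inputs.** Rate ratio 0.70, alpha 0.05, 15% attrition, 0.8 exacerbations per woman-year and half the women hormonal (all Section 7.7); two-sided testing (Section 9.3). Analysed: 575 × 0.85 = 488.75, about 489.

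**Assumptions, because the documents are silent.** One woman-year each; 0.8 is the higher of the two rates, so the lower is 0.8 × 0.70 = 0.56; plain Poisson variance; hormonal users divide evenly by type. For progestin-only versus combined I put 0.8 on progestin-only, in line with the hypothesis in Section 3.0.

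**Formula.** Power = Φ(|ln 0.70| / SE − 1.96), with SE² = 1/(n₁ × 0.56) + 1/(n₂ × 0.8) and |ln 0.70| = 0.3567.

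**Step 1: reproduce Table 8, taking its N as analysed.** Splits are hormonal/non-hormonal as a percentage of all women.

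| N | Stated | 50/50 | 50/29 | 50/30 | 77/23 |
|---|---|---|---|---|---|
| 450 | 0.77 | 0.867 | 0.769 | 0.776 | 0.776 |
| 475 | 0.80 | 0.884 | 0.791 | 0.798 | 0.797 |
| 500 | 0.82 | 0.899 | 0.811 | 0.818 | 0.817 |
| 525 | 0.83 | 0.913 | 0.829 | 0.836 | 0.835 |
| 550 | 0.85 | 0.924 | 0.846 | 0.852 | 0.852 |
| 575 | 0.86 | 0.935 | 0.861 | 0.867 | 0.867 |

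An equal split fails, and also fails with 15% removed first (0.808 to 0.893). About 50/29-30, leaving about 20% on nothing, fits every row within about one point. So does 77/23, and so does an equal split with the variance multiplied by about 1.28. The table alone cannot show which was used. The 80% at 575 enrolled agrees with Table 8's N as analysed, since 489 lies between the rows for 475 (0.80) and 500 (0.82).

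**Step 2: the contrast named in the 80% sentence.** Hormonal users: 0.50 × 488.75 = 244.4, so 122.2 per type.

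SE² = 1/(122.2 × 0.56) + 1/(122.2 × 0.8) = 0.01461 + 0.01023 = 0.02484; SE = 0.1576. Then 0.3567/0.1576 = 2.263, and power = Φ(0.303) = **0.62**. Dividing the types between 30:70 and 70:30 gives 0.52 to 0.62.

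**Step 3: each type versus non-hormonal users (Section 9.3).**
- Control 30% (146.6 women): SE² = 0.01461 + 1/(146.6 × 0.8) = 0.02314; SE = 0.1521; power = Φ(2.345 − 1.96) = **0.65**.
- Every other woman a control (244.4): SE² = 0.01461 + 1/(244.4 × 0.8) = 0.01973; SE = 0.1405; power = Φ(2.539 − 1.96) = **0.72**, the ceiling on this basis.

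**Step 4: the survey scenario.** About 60% using any method less about 50% hormonal leaves about 10% non-hormonal, or 48.9 women. Pooled contrast: SE² = 1/(244.4 × 0.56) + 1/(48.9 × 0.8) = 0.00731 + 0.02558 = 0.03288; SE = 0.1813; power = Φ(1.967 − 1.96) = **0.50**.

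**Step 5: sensitivity to follow-up.** Multiply the rates by t years, treating events as independent.

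| Years | Progestin-only vs combined (25/25) | Pooled, survey scenario (50/10) |
|---|---|---|
| 1 | 0.62 | 0.50 |
| 2 | 0.89 | 0.79 |
| 3 | 0.97 | 0.93 |
| 5 | >0.99 | 0.99 |

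If women differ in underlying rate, each group's variance gains a term d/n. For d = 0.5, 1.0 and 1.5 (my range; the documents give none), five years yields 0.87, 0.69 and 0.55 for progestin-only versus combined, and 0.74, 0.53 and 0.40 for the survey scenario.

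**The case against.** **Person-time.** The strongest reply is that the analysis is not confined to one year. Outcome data start in January 2010 and the Poisson model adjusts for follow-up. With two independent years, progestin-only versus combined reaches 0.89. This stands against any claim that the study cannot detect 0.70. It does not rescue Section 7.7, which states no follow-up. Section 9.3 censors women at method switch and pregnancy, and Step 5 shows how between-woman variation can cancel much of the gain.

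**Another split.** With 77/23 divided evenly, each type has 188.2 women. Then SE² = 1/(188.2 × 0.56) + 1/(188.2 × 0.8) = 0.01613 and power is Φ(2.808 − 1.96) = 0.80, so both stated figures would hold. But 77% hormonal contradicts the plan's own half and leaves no secondary control. Each type against the 23% control (112.4 women) would still have only 0.70: SE² = 0.00949 + 0.01112 = 0.02061, Φ(2.484 − 1.96).

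**Stronger readings that the documents do not support.** A reader might infer that Table 8 needs half the women as controls, or a variance inflation near 1.29; Step 1 shows it needs neither. A reader might also take 10% as the plan's control share and conclude that power is 0.41 to 0.50 (0.41 if the variance is inflated). That share is a difference between two rounded figures, one from a survey and one an enrolment expectation. Section 7.2 limits the population to women who have used contraception, so the survey's non-users may not carry over. If half means half of users, the split is 30/30 and one-year power is 0.70.

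**Work still open.** Section 7.7 says the statistical plan will be discussed further during the pilot. That lowers the cost of correction but does not supply the missing figures.

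**Conclusion.** The point holds as an unsupported power statement. On the one-year, plain Poisson basis that reproduces Table 8, with half the women hormonal and evenly divided by type, power at a rate ratio of 0.70 is about 0.62 for the contrast in the 80% sentence. For each type against a 30% control it is about 0.65, and at most 0.72. The figure of about 0.50 for the pooled primary comparison is a scenario that depends on the earlier survey's shares carrying over.

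None of these is the power of the design, because person-time, dispersion and censoring are unspecified and pull in opposite directions. The documents do establish two things without calculation: the 80% sentence and Table 8 name different contrasts, and the primary control has no stated size.

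**What to change.** In Section 7.7, replace Table 8 and the 80% sentence with power or detectable rate ratio for each planned contrast: pooled hormonal, combined and progestin-only, each versus non-hormonal and versus no contraception. Keep progestin-only versus combined only if it is a planned comparison. Base the figures on expected women or person-years per group, allowing for censoring at switch and pregnancy, and state the follow-up, the baseline rate and its group, and the dispersion assumed.

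Reconcile the contrast in the 80% sentence with Table 8's header. Reconcile the population in Section 7.2 with the never-used group in Section 8.1, since that decides who is in the secondary control.

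The cost is a rewrite of one section and a short recalculation. The downside is a less favourable stated power, particularly for the type-specific comparisons.

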7.8. Recruitment

We aim to recruit up to 625 female patients ages 18-45 years across 10 CF Centers. We may enroll an additional 25 participants to off-set participants who participated in a prior contraceptive study (4). The UW research team will ask each participating CF center research staff to invite all women ages 18-45 years who have been seen at their clinic within the last 2 years to participate in this retrospective contraceptive study. By inviting all potential qualified participants, we reduce selection bias of only those who physically come to the CF center on a regular basis. CF center research staff will send an email to all eligible women in their clinic and follow up with a phone call to recruit potential participants. In addition, women who come to the cF center research staff member.

7.8.1. Participant Incentives

Participants will be paid for enrolling into the study and completing the questionnaire (\$30). We have based this amount on the CFF hourly rate for research subjects of \$30/hour.

8.0. Methods: Assignment of interventions

8.1. Allocation

Participants will belong to a group based on their choice of contraception. Women with CF will be allocated to hormonal group (intervention), non-hormonal groups (control), and never used contraception.

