5.0. Trial Design

This is a non-randomized, non-interventional, observational cohort design among reproductive-aged women (ages 18-45 years) with CF. This protocol describes a pilot phase, as well as a larger retrospective approach.

We intend to ask about 625 female participants to provide information about their types of past contraceptive use from 2008 through the most recent data available from CFFPR (2018 or 2019). Before initiating our trial among up to 625 respondents, we intend to pre-test the survey questions on our self-respondent questionnaire among as many as 50 women with and without CF through CFF Community Voice, the Cystic Fibrosis Research, Inc. (CFRI), and the Cystic Fibrosis Reproductive and Sexual Health Collaborative (CFReSHC). Pre-testing our survey questions will help ensure contraceptive, pregnancy, and other reproductive health data from respondents for the larger phase of this study are as complete and accurate as possible.

Once the survey has been piloted and revised accordingly, we will collect past contraceptive, pregnancy and other reproductive health data from up to 625 women at 10 different CF centers. We may over-sample by 25 participants because it is possible that some participants from UW, UTSW and National Jewish may have participated in our earlier published study related to contraceptive use and CFFPR (4). Recruiting through the CF centers will help ensure that women with a confirmed diagnosis of CF respond to the finalized survey. We will link respondent self-reported contraceptive and reproductive health data with CFFPR clinical data. We will ask for EMR data from the 10 different CF centers to validate DXA scan results with findings regarding osteoporosis, osteopenia, and bone fracture in the CFFPR. We plan to randomly select about 10 consented subjects from each of the centers for the EMR DXA scan chart review. Because of our need to link questionnaires and clinical case report forms correctly to the same women with CF in the CFFPR clinical data, we need to request identifiable information, including the CFFPR member ID number.

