7.2. Eligibility Criteria

The study population will be women with CF who have used any form of contraception for protection against pregnancy or for treatment of dysmenorrhea, pelvic pain, abnormally heavy or prolonged menstrual bleeding, excessive uterine bleeding, endometriosis, acne, or amenorrhea.

Table 4: Full study inclusion and exclusion criteria

Inclusion Criteria
Females ages ≥ 18 and < 46 years at enrollment
Confirmed patients at one of the 10 participating CF centers (has been seen at least one time for a face-to-face
office visit at the CF center in the last 2 years)
CFFPR participant (noted as having a CFFPR ID number)
Has internet access
Has a functioning email addresses or may create a functioning email address at enrollment
Willing to consent to obtain request of their identified data from CFFPR
Willing to consent to their CF center to provide data related to contraceptive medication and DXA scan test results
as far back as 2013 in clinic EMR
Exclusion Criteria
Not in CFFPR
Non-functioning email address
History of organ transplant
Participant in pre-test phase of this study

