9.1.3. Patient Surveys

Table 10: Information in online, self-respondent surveys

Survey O	nce Enrolled
• Demog	graphics: marital status, race/ethnicity, and education
	nedical history: ever smoked, ever had a blood clot requiring anticoagulation, # PICC lines placed, PORT in (dates)
Medic	ation history: ever taken CFTR modulator (with start and stop dates)
-	al history: Tubal ligation, hysteroscopic sterilization, hysterectomy, bilateral oophorectomy, other operation as made it impossible to get pregnant
• Menst	rual history: menarche, regularity of menstruation, menopause
• Contra	aception questionnaire
•	Questions regarding types of contraception used since 2008, start and stop dates of each method or age at first/last use. Questions are based off of the National Survey of Family Growth (NSFG)
• Pregna	ancy history questionnaire

- - Includes number of pregnancies in lifetime, year(s) pregnant, outcome of pregnancy, whether pregnancy was planned or not
 - Additional questions to include for funded study ([name] and [name]): times visited CF center during pregnancy and type of provider who cared for participant during pregnancy, ART

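### The no-contraception control is never-users in 8.1 but women currently on no method in 9.3, and 7.2 read literally admits no never-users

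*Combined protocol and SAP*

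**What the plan says.** Four sections of the combined protocol and SAP bear on this group.

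- Section 8.1 (Allocation): "Women with CF will be allocated to hormonal group (intervention), non-hormonal groups (control), and never used contraception". The third group is defined by history.
- Section 9.3 (Statistical Methods): "We will also compare to women on no contraception, as the secondary control group". This describes a current state.
- Section 4.1 (Primary Study Objective) sets hormonal use against two comparators, the second being "non-contraceptive users (secondary control"). It gives no timing, so it fits either of the above.
- Section 7.2 (Eligibility Criteria): "The study population will be women with CF who have used any form of contraception for protection against pregnancy", or for one of several gynaecological or skin indications. Read literally, this admits no never-users, although Table 4 lists no such criterion.

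Exposure comes from the patient survey in 9.1.3: "Questions regarding types of contraception used since 2008, start and stop dates of each method or age at first/last use". Section 5.0 gives the exposure window as "past contraceptive use from 2008 through the most recent data available from CFFPR (2018 or 2019"). Section 9.3 starts outcome follow-up on January 1, 2010. Section 7.0 expects pre-testing to end in July 2020, so the full survey follows that date.

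**The concern.** A history and a current state select different women and different years. An analyst following 8.1 and one following 9.3 would build different control groups for the secondary comparison of the primary endpoint, and nothing in the plan says which governs. The choice could be made after results are seen.

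Timing adds a second problem. If never-use is judged at the survey, whether a woman's early non-use years count depends on what she did later in follow-up. That is harmless when starting a method has nothing to do with lung health. If it is related, in either direction, the never-use group is selected on something linked to the outcome.

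**Working it through.** **The two definitions side by side**

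| Non-use time since January 1, 2010 | 8.1, never used | 9.3, on no method |
|---|---|---|
| Woman reporting no method since 2008 | counted, unless 7.2 excludes her | counted |
| Years before a first method | no group | counted |
| Time between methods or after the last | no group | counted |

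Take a woman with no method in 2010 to 2015 who starts one in 2016. Under 9.3 she gives six control years. Under 8.1, fixed at the survey, she gives none. The survey's look-back also means that never would in practice be no reported use since 2008: a woman aged 45 in 2020 was 45 − 12 = 33 in 2008.

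**The plan's own figures.** The plan states no sample size or power for the secondary control. Table 8 concerns hormonal against non-hormonal users and does not enter this point.

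**How much control time is at stake.** The documents give 0.8 exacerbations per year (7.7). The rest is assumed: nine years of follow-up, survey at year 11, 30% already using a method in 2010, starting hazard h of 0.05 or 0.10 per year, no stopping. With annual steps and starting unrelated to exacerbations:

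- never-users at survey = 0.7 × exp(−11h)
- non-use years per woman = 0.7 × (1 − exp(−9h)) / (1 − exp(−h))
- share dropped by 8.1 = 1 − 9 × never-users / non-use years

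For h = 0.05: never-users 0.404; non-use years 5.20; share dropped 1 − 3.63/5.20 = 0.30.
For h = 0.10: never-users 0.233; non-use years 4.37; share dropped 1 − 2.10/4.37 = 0.52.

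The control term in the variance of the log rate ratio is 1/events, so at equal rates it grows by 5.20/3.63 = 1.4 or 4.37/2.10 = 2.1 times. Stopping would add time after methods to the dropped part.

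**Whether the ratio moves.** The next model is a simulation of 1,000,000 women per row with the same set-up. The true rate is 0.80 off method and 0.56 on a hormonal method, so the true ratio is 0.70. The hazard of starting is multiplied by m after a year with an exacerbation. No underlying severity difference is built in.

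| h | m | Never-users | Share dropped | Control rate 9.3 | Control rate 8.1 | Ratio 9.3 | Ratio 8.1 |
|---|---|---|---|---|---|---|---|
| 0.05 | 0.5 | 0.472 | 0.225 | 0.801 | 0.809 | 0.700 | 0.692 |
| 0.05 | 1 | 0.404 | 0.301 | 0.800 | 0.800 | 0.700 | 0.700 |
| 0.05 | 2 | 0.300 | 0.429 | 0.799 | 0.781 | 0.701 | 0.717 |
| 0.10 | 0.5 | 0.317 | 0.407 | 0.799 | 0.817 | 0.700 | 0.685 |
| 0.10 | 1 | 0.233 | 0.519 | 0.800 | 0.800 | 0.700 | 0.700 |
| 0.10 | 2 | 0.129 | 0.685 | 0.800 | 0.765 | 0.700 | 0.732 |

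For example, in the last row 0.56/0.765 = 0.732. The 9.3 control recovers 0.70 throughout. The 8.1 control moves either way, by at most about 0.03.

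**Adding unmeasured severity.** With gamma frailty of variance 0.5, h = 0.10 and a starting hazard proportional to frailty^0.25 (sicker women start sooner), the crude ratios are 0.84 (9.3) and 0.93 (8.1). With frailty^−0.25 (sicker women start later) they are 0.58 and 0.54. The 8.1 ratio is therefore 0.93/0.84 = 1.11 or 0.54/0.58 = 0.93 times the 9.3 ratio. Across all dependent frailty scenarios run with a true ratio of 0.70, the 8.1 ratio was about 12% lower to 37% higher than the 9.3 ratio. In a separate frailty simulation with no true effect, both ratios were 1.0 when starting was unrelated to health. With dependence, examples were 0.91 (9.3) against 0.81 (8.1), and 1.09 against 1.26 with the sign reversed.

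**The case against.** The best defence is that 8.1 is one sentence of orientation and that the comparison is specified in 9.3. Section 8.1 does not call its third group the secondary control; that follows only because no other group is left. It does not say when never-use is fixed either, and the start and stop dates would allow time to be classed as not yet used. So a reader might infer that the plan discards the early years of later starters, but no passage says so. That objection stands, and the selection problem is conditional on applying 8.1 as written.

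A reader might also infer that 4.1 and 9.3 already specify person-time on no method. They do not. Section 4.1 gives no timing. Section 9.3 names a current state and adjusts for individual follow-up time, but never says that membership is reassessed. It censors women who switch method types without saying whether a first start counts as a switch.

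A third tempting reading is that the never-use control exaggerates a hormonal benefit. The documents do not say whether sicker women start sooner or later, and the direction reverses with that assumption. The frailty figures are also crude, whereas the plan adjusts for the Table 5 covariates, and part of their distance from the true value is confounding shared by both definitions. The annual model has no confounder to adjust for, so its gap is due to selection alone, but that gap is small.

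Finally, 7.2 read literally leaves the never-used group empty, in which case no never-use ratio could be computed. That does not remove the conflict. It means that a third section must be reconciled.

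**Conclusion.** The conflict between 8.1 and 9.3 is real, unresolved in the documents, and compounded by 7.2. It should be settled before analysis, because the secondary control is named in the primary objective. If 8.1 is applied as written at the survey, part of the non-use time since 2010 has no control group and membership depends on later behaviour. The share dropped was 22% to 68% in the simulations without frailty, under assumed starting rates that the documents do not give.

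The effect on the rate ratio is a possibility, not a certainty. It is nil if starting a method is unrelated to exacerbations or severity, and can go either way if it is related. The figures above illustrate the mechanism and do not estimate the bias in this study. The background figure that "only about 60% of reproductive—aged women with CF are using contraception" implies that about 100 − 60 = 40% were not using a method at that survey, but the documents do not say how many of those were never-users. The primary comparison with non-hormonal users and Table 8 do not depend on this point.

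**What to change.** Use one definition in 4.1, 7.2, 8.1 and 9.3: the secondary control is person-time on no contraceptive method, classified at each point in follow-up from the dated method history, with follow-up in that group ending when a method starts. State in 9.3 how time is assigned when a woman gives only age at first or last use, since the survey allows that in place of dates.

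Reconcile the opening sentence of 7.2 with Table 4. If it is changed to admit never-users, report women with no reported use since 2008 as a sensitivity group only, under that label.

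The cost is a wording change in four sections and time-split records in the analysis dataset. No new data are needed, because the survey already collects the method history.
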